	PFS according to RECIST 1.1 assessed by Investigator	Population/Treatment: Same as #1 Intercurrent Event Strategy: 
 Death within 2 missing scheduled tumor assessments after last evaluable assessment or start of study intervention will be considered as event (composite strategy) Discontinuation of treatment: ignoring the intercurrent event (treatment policy strategy) Start of subsequent anticancer therapy: ignoring events after the start of a new anticancer therapy (hypothetical strategy) Population-level Summary: Kaplan-Meier estimates including associated statistics	4
	Locoregional control (LRC) according to RECIST 1.1 assessed by Investigator	Population/Treatment: Same as #1 Intercurrent Event Strategy: 
 Death: Assessments before death will be used (treatment policy strategy) Discontinuation of treatment: ignoring the intercurrent event (treatment policy strategy) Start of new anticancer therapy: ignoring events after the start of a new anticancer treatment (hypothetical strategy) Population-level Summary: Same as #4	5
To evaluate time to subsequent cancer treatments in participants treated with xevinapant when added to weekly cisplatin-based CRT in LA SCCHN	Time to subsequent systemic cancer treatments	Population/Treatment: Same as #1 Intercurrent Event Strategy/ Population-level Summary: Same as #5	6

Overall Design:

This is a multicenter, single arm, open label, Phase 1b study.

Brief Summary: The purpose of this study is to evaluate the tolerability and safety of xevinapant when added to weekly cisplatin-based concurrent CRT in the treatment of participants with unresectable locally advanced squamous cell carcinoma of the head and neck, suitable for definitive chemoradiotherapy.

Study details include:

- Study duration: participants to be followed until the last on-study participant reaches his/her 18-month post-first treatment visit (EOS) a decision to end the study has been triggered, or until premature discontinuation from study, whichever occurs first.
- Treatment duration: 18 weeks, consisting of six 3-week cycles.

- Visit frequency: One to 3 visits a week during combination therapy period, once every 3 weeks during xevinapant monotherapy period, and every 3 months during the Follow-up period until EOS.

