¹⁸F-FDG=[¹⁸F]Fluorodeoxyglucose, CT=computed tomography, ECG=electrocardiogram, ECOG PS=Eastern Cooperative Oncology Group Performance Status, HBV=Hepatitis B Virus, hCG=human Chorionic Gonadotropin, HCV=Hepatitis C Virus, HIV=human immunodeficiency virus, HPV=human papillomavirus, ICF=informed consent form, IHC=immunohistochemistry, iv=intravenous, MRI=magnetic resonance imaging, OPC=oropharyngeal cancer, PET=positron emission tomography, POCBP=Person of Childbearing Potential, SARS-CoV 2=Severe acute respiratory syndrome coronavirus 2.

Table 2 Schedule of Activities (Combination Treatment Period [Cycles 1 to 3])

Study Period	Combination Therapy Period (Xevinapant, Cisplatin, and IMRT)																				Notes		
Cycle	Cycle 1								Cycle 2								Cycle 3						
Cycle Day	1	2	4	8	9	11	15	16	18	1	2	4	8	9	11	15	16	18	1	2	4	8	
Study Week	1	1	1	2	2	2	3	3	3	4	4	4	5	5	5	6	6	6	7	7	7	8	
Study Day	1	2	4	8	9	11	15	16	18	22	23	25	29	30	32	36	37	39	43	44	46	50	
Visit Window (days)	- 3									± 3									± 3				
Physical exam	X									X									X			See Section 8.2.1	
ECOG PS	X									X									X				
Vital Signs	X	X			X			X		X	X			X			X		X	X		Including Weight at CxD1	
ECG	X			X																			
Audiometry				(X)			(X)			(X)			(X)			(X)		(X)		(X)		Only if clinically indicated. See Section 8.2.7	
Laboratory assessments																							
Blood hematology	X			X			X			X			X				X		X		X	Local laboratory	
Blood biochemistry – full panel	X									X								X				Local laboratory	
Blood biochemistry – minimum panel				X			X						X				X					Local laboratory	
CCI																							
Pregnancy test	X									X								X				Local laboratory	
Urinalysis	X									X								X				Local laboratory	

Study Period	Combination Therapy Period (Xevinapant, Cisplatin, and IMRT)																					Notes		
Cycle	Cycle 1										Cycle 2										Cycle 3			
Cycle Day	1	2	4	8	9	11	15	16	18	1	2	4	8	9	11	15	16	18	1	2	4	8		
Study Week	1	1	1	2	2	2	3	3	3	4	4	4	5	5	5	6	6	6	7	7	7	8		
Study Day	1	2	4	8	9	11	15	16	18	22	23	25	29	30	32	36	37	39	43	44	46	50		
Visit Window (days)	-3									± 3									± 3					
Disease assessments																								
Nutritional status	X									X									X				See Section 6.8.4 .1	
CT or MRI																							See Section 8.1	
Clinical tumor assessment																							See Section 8.1	
Treatments																								
Xevinapant	From Day 1 to 14									From Day 1 to 14									From Day 1 to 14				See Section 6.5.1	

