6.5.3.4 Management of Acute "in Radiation Field" Toxicity

If dermatitis, mucositis, or dysphagia occurs, the possibility of IMRT interruption should be assessed according to their severity. Institutional guidelines on prophylaxis and dental hygiene will be followed for management of skin and mucosal toxicity.

For any other degree of minor toxicity, the necessary support measures must be taken to ensure treatment continuity ([Peterson 2015](#)).

In the event of mucositis, the following recommendations will be considered:

- Rapid escalation of analgesics using the World Health Organization cancer pain relief ladder ([WHO 2018](#)).
- Enteral or parenteral nutritional support according to the institutional guideline. Enteral nutritional support is strongly recommended if weight loss is $\geq 5\%$. If the weight loss is $\geq 10\%$, the use of a nasogastric or gastrostomy tube must be implemented as quickly as possible ([Elad 2019](#)) and access to adequate nutritional support needs to be secured by the Investigator.

The management of radiation dermatitis should be based on the severity of symptoms, as determined by Radiation Therapy Oncology Group and should follow the recommendations by the Supportive Care Guidelines Group.

6.5.3.5 **End of Radiotherapy**

Radiotherapy will be administered until completion of the IMRT dose and schedule (see [Table 9](#)) planned in the study or until any of the study intervention discontinuation criteria described in Section [7.1](#) occur.

Note: Radiotherapy discontinuation will not result in xevinapant discontinuation or chemotherapy discontinuation. See further Section [6.5.1.3](#).

Treatment interruption and permanent discontinuation of any of the components of the study intervention is to be recorded in the Dosing CRF of each component of the study intervention. For each action, the reason must be recorded.

Discontinuation from study intervention does not mean discontinuation from the study. Procedures to be followed in the event of a study intervention discontinuation are presented in Section [7.1](#).

Procedures for discontinuation from study (not only study intervention) are described in Section [7.2](#).

6.6 **Continued Access to Study Intervention After the End of the Study**

Not applicable

6.7 **Treatment of Overdose**

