7.3 Lost to Follow-Up

A participant will be considered lost to follow-up if repeatedly failing to return for scheduled visits and is unable to be contacted by the study site.

The following actions will be taken if a participant fails to return to the clinic for a required study visit:

- The site will attempt to contact the participant and reschedule the missed visit as soon as possible, counsel the participant on the importance of maintaining the assigned visit schedule and ascertain if the participant wants to or will continue in the study.
- Before a participant is deemed “lost to follow-up”, the Investigator or designee will make every effort to regain contact with the participant: 1) where possible, make 3 telephone calls; 2) if necessary, send a certified letter (or an equivalent local method) to the participant’s last known mailing address, and 3) if a participant has given the appropriate consent, contact the participant’s general practitioner or caretaker (where allowed by local regulations) for information. These contact attempts will be documented in the participant’s medical record.
- If the participant continues to be unreachable, he/she will be deemed as “lost to follow-up”.

8 Study Assessments and Procedures

- Study assessments and procedures and their timing are summarized in the SoA. It may be necessary to perform these assessments at unscheduled timepoints if deemed clinical necessary by the Investigator.
- **No** protocol waivers or exemptions are allowed.
- Immediate safety concerns are discussed with the Sponsor immediately upon occurrence or awareness to determine if the participant will continue or discontinue study intervention.
- Adherence to the study design requirements, including those specified in the SoA, is essential, and required for study conduct.
- All screening evaluations will be completed and reviewed to confirm that potential participants meet all eligibility criteria. The Investigator will maintain a screening log to record details of all participants screened, to confirm eligibility, and if applicable, record reasons for screening failure.
- Prior to performing any study assessments that are not part of the participant's routine medical care, the Investigator will obtain written informed consent as specified in [Appendix 5](#).

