8.2.2 Vital Signs

- Blood pressure and participant's position during measurement; pulse; respiratory rate; temperature and location of measurement, weight, and height (at Screening only) will be measured and recorded.
- Blood pressure and pulse measurements will be preceded by at least 5 minutes of rest for the participant in a quiet setting without distractions (e.g. television, cell phones) and measured with an automated device. Manual techniques will be used only if an automated device is not available.

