9.1 Statistical Hypotheses

No formal statistical hypothesis will be tested, as the study is designed to be exploratory.

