Appendix 4 Cisplatin Hydration Guidelines

Adequate hydration must be maintained from 2 to 3 hours prior to administration until minimum of 2 hours after the administration of cisplatin (SmPC TEVA v6.0 2019).

Hydration is necessary to cause sufficient diuresis during and after treatment with cisplatin. It is realized by intravenous infusion of one of the following solutions:

- Sodium chloride solution 0.9%
- Mixture of sodium chloride solution 0.9% and glucose solution 5% (1:1).

Hydration prior to treatment with cisplatin:

- Intravenous infusion for a period of 2 to 3 hours, with a total amount of at least 1 L.

Hydration after termination of the administration of cisplatin:

- Intravenous infusion of another 2 liters for a period of at least 2 hours.
- Additional hydration on days 2 and 3 post-cisplatin dosing as per institutional guidelines.

Efforts to maintain urine output to 100 mL/hour on the day of cisplatin administration is important and forced diuresis should be required as appropriate, by taking the increase or decrease in in-out balance and body weight into account. Forced diuresis may be realized by intravenously administering 37.5 g mannitol as a 10% solution (375 mL mannitol solution 10%), or by administration of a diuretic if the kidney functions are normal. The administration of mannitol or a diuretic is also required when the administrated cisplatin dose is higher than 60 mg/m² of body surface.

It is necessary that the participant drinks large quantities of liquids for 24 hours after the cisplatin infusion to ensure adequate urine secretion.

Hydration guidelines may be modified at the discretion of the treating physician provided adequate pre and postcisplatin hydration is achieved, and renal function remains adequate.

Consider a More Extensive Hydration Regimen Under Certain Circumstances:

Additional pre-hydration with normal saline iv or orally at minimum in the 48 hours preceding cisplatin infusion and a more extensive posthydration regimen (recommended 1,000-1,500 mL on days 2 to 3 post-cisplatin dose) is requested whenever possible in those participants with risk factors for renal toxicity, e.g. proteinuria, diabetes, and hypertension.

CCI

Attention should also be paid to any signs of dehydration (insufficient urine outputs) or conditions leading to a potential dehydration like diarrhea, vomiting, undernutrition, infection/fever.

CCI

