## 15.5 Vital Signs

Vital sign summaries will include all vital sign assessments from the on-treatment period. All vital sign assessments will be listed, and those collected outside the on-treatment period will be flagged in the listing.

All vital sign parameters will be summarized using descriptive statistics (mean, SD, median, Q1, Q3, minimum, and maximum) presenting baseline value, maximum on treatment, and minimum on treatment as well as their changes to baseline.

The maximum changes of vital sign measurements screening/baseline to maximum changes after start of 1st study intervention will be grouped as follows:

Body temperature increase	< 1°C , 1-<2°C , 2-<3°C, $\geq$ 3 °C
Heart rate increase from baseline <100 bpm ; $\geq$ 100 bpm	$\leq$ 20 bpm, >20 – 40 bpm, >40 bpm
Heart rate decrease from baseline <100 bpm ; $\geq$ 100 bpm	$\leq$ 20 bpm, >20 – 40 bpm, >40 bpm
SBP increase from baseline <140 mmHg; $\geq$ 140 mmHg	$\leq$ 20 mmHg, >20 – 40 mmHg, >40 mmHg
SBP decrease from baseline <140 mmHg; $\geq$ 140 mmHg,	$\leq$ 20 mmHg, >20 – 40 mmHg, >40 mmHg

DBP increase from baseline <90 mmHg; $\geq$ 90 mmHg	$\leq$ 20 mmHg, >20 – 40 mmHg, >40 mmHg
DBP decrease from baseline <90 mmHg; $\geq$ 90 mmHg,	$\leq$ 20 mmHg, >20 – 40 mmHg, >40 mmHg
Respiration rate increase from baseline <20 bpm ; $\geq$ 20 bpm	$\leq$ 5 bpm, >5 – 10 bpm, >10 bpm
Respiration rate decrease from baseline <20 bpm ; $\geq$ 20 bpm	$\leq$ 5 bpm, >5 – 10 bpm, >10 bpm

For each participant the worst on-treatment value will be calculated. For the definition of baseline values see Section 9.2. Missing values will define a separate category.

The following summaries will be prepared for vital sign parameters as grouped above:

- Maximal Shifts (changes in categories)
- Listing of highest change per participant

An additional participant data listing will present all changes from baseline reported in the highest categories.

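### During chemoradiotherapy the Schedule of Activities requires weight only every three weeks, which does not match the protocol's own 5% and 10% weight-loss triggers or its use of body weight on cisplatin days

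*Protocol*

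**What the plan says.** - **Schedule.** Protocol Section 1.3, Table 2 places vital signs on study Days 1, 2, 9, 16, 22, 23, 30, 37, 43 and 44. The note on that row is "Including Weight at CxD1", so weight is required on Days 1, 22 and 43. Table 3 continues on Days 64, 85, 106 and 134. Nutritional status in Table 2 is also assessed only on Day 1 of each cycle.
- **Content of vital signs.** Section 8.2.2 gives the list, ending "temperature and location of measurement, weight, and height (at Screening only) will be measured and recorded". Only height carries a visit restriction. The notes in Tables 1 and 3 include weight without one.
- **Timing.** The opening of Section 8 states: "Study assessments and procedures and their timing are summarized in the SoA".
- **Rules that use weight.** Section 6.5.3.4, under mucositis, strongly recommends enteral support at 5% loss. At 10% it says "the use of a nasogastric or gastrostomy tube must be implemented as quickly as possible". Section 6.8.4.1 recommends a feeding tube for marked swallowing difficulty and/or loss beyond 5% to 10%. Appendix 4 manages diuresis on the day of cisplatin "by taking the increase or decrease in in-out balance and body weight into account".
- **Analysis.** SAP Section 15.5 summarises vital sign parameters "presenting baseline value, maximum on treatment, and minimum on treatment as well as their changes to baseline". Protocol Section 9.4.2 names weight separately and summarises it by timepoint. SAP Section 7.1 keeps only vital-sign summary statistics over time for the synoptic report.

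**The concern.** Table 2 covers the radiotherapy period, and it is the only one of the three schedule tables that narrows when weight is taken. Participants attend one to three times a week in this period (Section 1.1), yet required weights are no more frequent than in monotherapy. The protocol's nutrition rules depend on percentage weight loss, and at the higher threshold they call for prompt action. Section 2.3 reports weight decrease as more frequent with xevinapant than with placebo, and Section 4.2.1 says the importance of nutritional monitoring was carried into this design from patient interviews.

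Two things are at stake. A participant could cross a trigger with no protocol-required measurement to show it until the next cycle starts. The trial data on weight loss, a known signal for this drug, would also be sparse in the weeks when loss is most likely to build up.

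**Working it through.** No error rate or sample-size figure enters this point. Section 9.1 says "No formal statistical hypothesis will be tested, as the study is designed to be exploratory", and the DLT-like definition in Section 8.2.5.1 does not use weight.

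**1. Gaps between required weights.** The cycle length is given in Section 1.1: "Treatment duration: 18 weeks, consisting of six 3-week cycles". From Tables 2 and 3:
- 22 − 1 = 21; 43 − 22 = 21; 64 − 43 = 21 days. This reproduces the nominal three-week interval.
- Section 1.3 allows −3 days at C1D1 and ±3 days at later Day 1 visits. The widest gap is 21 + 3 + 3 = 27 days.

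**2. Cisplatin days.** Infusions are planned on Days 2, 9, 16, 23, 30, 37 and 44. Each has a vital-sign set and none has a scheduled weight. Days 2, 23 and 44 come one day after a required weight. On the other four the last required weight is 8 days old (9 − 1 and 30 − 22) or 15 days old (16 − 1 and 37 − 22).

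**3. Weight at every vital-sign set in Table 2.** Gaps from Day 1 become 1, 7, 7, 6, 1, 7, 7, 6 and 1 days up to Day 44, then 20 days to Day 64. Weights over Days 1 to 44 rise from 3 to 10, and the largest gap in that stretch falls from 21 to 7 days. The 20-day gap remains because no vital signs are scheduled between Days 44 and 64. A weight at the existing C3D8 visit (Day 50) would split it into 6 and 14 days.

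**4. Delay in seeing a trigger.** The documents give no rate of weight loss, so a steady loss from Day 1 is assumed over a range of rates. Crossing day = 1 + 7 × threshold ÷ weekly loss. Delay = next weight day − crossing day.

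| Loss per week | Trigger | Crossed on day | First required weight, Table 2 note | First weight if taken at every vital-sign set |
|---|---|---|---|---|
| 0.5% | 5% | 71 (after radiotherapy) | – | – |
| 1% | 5% | 36 | Day 43 (7 days) | Day 37 (1 day) |
| 1.5% | 5% | 24.3 | Day 43 (18.7 days) | Day 30 (5.7 days) |
| 1.5% | 10% | 47.7 | Day 64 (16.3 days) | Day 64 (16.3 days) |
| 2% | 5% | 18.5 | Day 22 (3.5 days) | Day 22 (3.5 days) |
| 2% | 10% | 36 | Day 43 (7 days) | Day 37 (1 day) |

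The 10% row at 1.5% per week gains nothing from the vital-sign visits. Only a C3D8 weight would bring it forward, to Day 50 (50 − 47.7 = 2.3 days).

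**5. Average delay.** If crossings are spread evenly over Days 1 to 64, the mean delay is the sum of squared gaps ÷ (2 × 63):
- Table 2 note: 3 × 441 ÷ 126 = 10.5 days.
- Every vital-sign set: 671 ÷ 126 = 5.3 days.
- C3D8 added: 503 ÷ 126 = 4.0 days.

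This describes the schedules only. It treats a crossing in the first days as no less likely than a later one, which is not realistic for a 5% or 10% loss.

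**6. Maximum weight loss.** Assume steady loss of 0.5% to 2% per week to a lowest point on Day 50, then recovery of 0 to 1% per week. Day 1 weights understate the maximum loss by 0 to 2.0 percentage points. Weights at every vital-sign set understate it by 0 to 1.7 points. At 2% per week with 1% recovery, for example, the true maximum is 14.0%, against 12.0% and 12.3% observed.

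**The case against.** The strongest reply is that nothing contradicts anything. Section 8.2.2 says what vital signs contain, Section 8 leaves timing to the schedule, and the schedule is explicit. A reader might infer that Section 8.2.2 demands weight in every vital-sign set; it does not say so. This part of the objection stands, and the point is one of ambiguity.

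Second, required data collection is not the only weighing that happens. Participants come for radiotherapy five days a week, Section 1.3 permits unscheduled assessments, and the 5% and 10% thresholds in Section 6.5.3.4 are recommendations for mucositis, with support given by institutional guideline. In Section 6.8.4.1 swallowing difficulty is another route to the same action. Appendix 4 describes same-day fluid care that the treating physician may modify. A reader might infer that a crossed trigger will go unseen for three weeks. The documents support only that no required weight would show it between Day 1 visits. The Radiotherapy Manual and the redacted dose-modification tables might also ask for weights; that cannot be checked here. Even so, the extra weighing visible in the protocol is discretionary, and nutritional status follows the same three-week pattern.

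Third, a reader might conclude that the analysis will miss the lowest on-treatment weight. That goes too far. SAP Section 15.5 does not name weight, protocol Section 9.4.2 summarises it by timepoint, SAP Section 7.1 keeps only statistics over time, and later weights on Days 64, 85 and 106 may contribute. Nor should Day 64 be counted as a fourth combination-period weight: it is C4D1, in monotherapy. The combination period has three.

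**Conclusion.** The point holds as a mismatch between the schedule and the rules that rely on it. Required weights are 21 days apart (up to 27 with windows), while the protocol acts on 5% and 10% loss and considers body weight on cisplatin days without a scheduled weight on any of them.

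The practical size depends on an assumed linear loss rate. For the 5% trigger, the difference between the two schedules ranges from none (2% per week, or 0.5% where the trigger is not reached during radiotherapy) through about 6 days (1%) to about 13 days (1.5%: 18.7 − 5.7). Maximum weight loss may be understated, by up to about 2 percentage points under the assumptions shown, but this is not certain. The primary endpoint and the sample size are unaffected. This is an inexpensive improvement to safety data collection; it does not threaten the trial's main conclusion.

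**What to change.** Reconcile the Table 2 note with Sections 8.2.2, 6.5.3.4 and 6.8.4.1 and Appendix 4 by recording weight at the vital-sign visits already in Table 2 (C1D2, C1D9, C1D16, C2D2, C2D9, C2D16 and C3D2, as well as Day 1 of each cycle). Section 8.2.2 should point to the schedule for timing, so that the two read the same way.

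As a separate and optional addition, record weight at the existing C3D8 visit. Reconciling the texts does not by itself require this, but without it the 20-day gap from Day 44 to Day 64 remains.

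The cost is one table note and one data field at visits that already take place, with a few more entries per participant. The nutrition, hydration and dosing rules stay as they are.

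SAP Section 7.1 has already reduced the study to a synoptic report. If the schedule can no longer change, the clinical study report should state that weight was required only every three weeks during chemoradiotherapy and that maximum loss may therefore be understated.

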2.1 Study Rationale

Head and neck cancer is a common cancer; representing approximately 5% of all cancer cases worldwide with an annual incidence of over 878,000 cases and a mortality estimated at 444,000 deaths per year in 2020 (Sung 2021, Ferlay 2021). Definitive treatment options for LA SCCHN, such as surgery, can cure some patients, but can also lead to severe limitations in feeding (chewing and swallowing), speaking, and physical appearance that can impair social functioning and cause severe psychological stress (Hernandez-Vila 2016, NCCN v1 2023). Among conservative (nonsurgical) treatments, the most widely used standard regimen in this setting consists of high-dose (100 mg/m^2) cisplatin administered Q3W for up to 3 cycles, combined with approximately 70 Gy radiation delivered in 1.8 to 2.0 Gy daily fractions. Although associated with increased toxicity compared to RT alone, this combination is also associated with increased local control rates and OS (Oun 2018). However, Q3W cisplatin (100 mg/m^2) is associated with toxicities such as nephrotoxicity, hematotoxicity, and ototoxicity leading to low treatment adherence. Weekly cisplatin (CCI mg/m²), administered every week (QW) for up to 7 weeks, is one of the commonly used alternative regimens for Q3W cisplatin (100 mg/m^2) with potentially milder renal and ototoxicity, CCI.

Furthermore, weekly cisplatin at CCI mg/m² requires a less intense hydration regimen compared to high-dose Q3W cisplatin (NCCN v1 2023, Machiels 2020, Baum 2019).

Xevinapant is an inhibitor of IAPs that has been shown in nonclinical in vitro and in vivo models to have both chemo- and radiosensitizing potential as well as immunomodulatory potential (Serova 2014, Matzinger 2015, Tao 2019). In unresected LA SCCHN patients, the addition of xevinapant to SoC CRT recently showed a statistically significant and clinically meaningful improvement in locoregional control at 18 months compared to placebo with SoC CRT (Sun 2020).

Following the 36-month analysis, PFS also showed a clinically meaningful improved benefit from xevinapant versus placebo. Furthermore, a clinically relevant improvement in 5-year OS using xevinapant combined with CRT vs the control group was recently presented (Tao 2023). The findings of this study are currently being confirmed in a Phase 3 study using standard Q3W cisplatin-based chemoradiation in combination with xevinapant (Debio 1143-SCCHN-301/ MS202359_0006 [TrilynX]).

The purpose of this study is to evaluate the tolerability and safety of xevinapant when added to weekly cisplatin (CCI mg/m²) based concomitant CRT in the treatment of participants with unresected LA SCCHN.

